## **Study Period**

**Retrospective Data Period:** January 2015 – June 2015

**Prospective Data Period:** After the clinicians have completed the Parkinson's Disease Inpatient Clinical Knowledge and Management Program and the WatchRx Smartwatch is integrated within medication administration for PD medications

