## **Retrospective Study Period**

Version 5 Revised 5/9/2019

Data collection of adult patients admitted with a primary and secondary diagnosis of Parkinson's disease during January – June 2015.

- Data will be extracted from the EPIC (current EMR system at Hackensack University Medical Center).
- Business intelligence will run the data and create reports with the specific data points mentioned above prior to providing it to the study team for further statistical analysis.

Data collected from the automatic dispensing cabinet barcoding database will verify accuracy and timeliness of medication.

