## **Prospective Study Period**

Data collection starting after completion of the Parkinson's Disease Inpatient Clinical Knowledge and Management Program for staff nurses, advanced practice nurses (APN), nursing assistants, patient care technicians, case managers, adult inpatient physician assistants, pharmacists, occupational therapists, physical therapists, nurse educators, and dietitians.

- Data will be extracted from EPIC and WatchRx records from the Watch Rx Web Interface.

Data collected from the automatic dispensing cabinet barcoding database will verify accuracy and timeliness of medication.

- Unstructured data will be collected by the principle investigator (PI), designees inclusive of study staff through focused chart review on 150 patients.
- Data will be analyzed for objectives and endpoints.

This data will compare prevalence of medication errors, complications associated with administration of contraindicated medications and timing of medications, falls and falls with

injury, positive CAM and Mini-Cog Scores, length of stay and cost per case in the study population. This phase will also assess the knowledge of the clinicians regarding the basic aspects of Parkinson's Disease inpatient management, the Parkinson's Disease Inpatient Clinical Knowledge and management program and integration of the smartwatch into the PD medication management.

- Parkinson's Disease Knowledge Assessment Survey (Appendix A)
- Parkinson's Disease Inpatient Clinical Knowledge and Management Program (Appendix B)

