## **Sample Size Calculation**

A total of 433 patients were admitted to Hackensack University Medical Center with a diagnosis of PD in the year 2014. A convenience sample of 300 patients, 150 patients in the prospective phase and 150 patients in the retrospective phase, and approximately 346 clinicians, before and after implementing the Parkinson's Disease Inpatient Clinical Knowledge and Management education program will be enrolled in the study.

The sample of clinicians will include physician's assistant, advanced practice nurses, staff nurses, nurse educators, case managers, dietitians, pharmacists, physical therapist and occupational therapist. (Table 1)

Categories	Overall population	Sample population	Percentage (Sample size)
Staff Nurses Adult (Inpatient Units)	1931	100	5 %
Nursing Assistants	277	N/A	
Patient Care Technicians	165	N/A	
Advanced Practice Nurses (Adult Inpatient Units)	107	87	81%
Case Managers(Adult Inpatient Units)	48	48	100%
Nurse Educator Adult Inpatient	20	19	95%
Physician's Assistant Adult Inpatient	73	40	54%
Dietitians	17	17	100%
Pharmacists	119	12	11%
Physical Therapist	17	17	100%
Occupational Therapists	6	6	100%

Table 1

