## Data Analysis

The summary of the demographic characteristics will be presented. Continuous variables will be summarized using mean (SD) or median (interquartile range) depending on whether or not the data follow the normal distribution. Categorical variables will be summarized by frequency (percentage). Comparison of continuous variables between any independent groups will be examined using two-sided t-test or two-sided Wilcoxon rank sum test, analysis of variance (ANOVA) or Kruskal-Wallis test followed by pairwise tests, as appropriate. Categorical variables will be examined using Fisher's exact test or Pearson's Chi-square test, as appropriate.

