**P.I.C.K. WatchRx Smartwatch Nurse Cleaning Log**  
**Appendix F**

Date (MM/DD/YYYY)	Watch cleaned with SuperSani Cloth	Unit	End of Shift/Handoff (Time)	Signature
	 Yes  No		RN Day Shift _____ PRINT NAME _____  RN Night Shift _____ PRINT NAME _____	
	 Yes  No		RN Day Shift _____ PRINT NAME _____  RN Night Shift _____ PRINT NAME _____	
	 Yes  No		RN Day Shift _____ PRINT NAME _____  RN Night Shift _____ PRINT NAME _____	
	 Yes  No		RN Day Shift _____ PRINT NAME _____  RN Night Shift _____ PRINT NAME _____	
	 Yes  No		RN Day Shift _____ PRINT NAME _____  RN Night Shift _____ PRINT NAME _____	
	 Yes  No		RN Day Shift _____ PRINT NAME _____  RN Night Shift _____ PRINT NAME _____	
	 Yes  No		RN Day Shift _____ PRINT NAME _____  RN Night Shift _____ PRINT NAME _____	
	 Yes  No		RN Day Shift _____ PRINT NAME _____  RN Night Shift _____ PRINT NAME _____	

Page 1\_\_ of \_\_

©Institute for Evidence Based Practice & Nursing Research  
 Original 5/9/19

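### Cost per case is to be compared between January–June 2015 and a phase that appears to start in 2019 or later, with no common price year; if the figures are nominal, the later period is biased upward

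*Combined protocol and SAP*

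**What the plan says.** The Prospective Study Period section says the data will be used to compare several outcomes, ending with "positive CAM and Mini-Cog Scores, length of stay and cost per case in the study population". The PICK Data Collection Tool in Appendix F has a column for cost per case. The extracted header shows no column for price year or index.

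The comparator is fixed in Study Period as "January 2015 – June 2015". The prospective period has no calendar dates. It begins "After the clinicians have completed the Parkinson's Disease Inpatient Clinical Knowledge and Management Program and the WatchRx Smartwatch is integrated within medication administration". Two dates bear on when that is: the protocol is marked "Version 5 Revised 5/9/2019" and describes the prospective procedures in the future tense, and the nurse cleaning log for the smartwatch is marked "Original 5/9/19".

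The sample is "A convenience sample of 300 patients, 150 patients in the prospective phase and 150 patients in the retrospective phase". The method for a continuous variable is in Data Analysis: "Comparison of continuous variables between any independent groups will be examined using two-sided t-test or two-sided Wilcoxon rank sum test", with ANOVA or Kruskal-Wallis as the multi-group versions. No section mentions inflation, a price index, a price year or constant dollars. None says whether cost per case means cost or charge, or which accounting source supplies it.

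Cost per case does not appear in the hypotheses, the objectives, the endpoint lists or the Measurements section.

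**The concern.** Falls, delirium scores and length of stay are counted in the same unit in both periods. A dollar figure is not, unless someone makes it so. If each admission carries the dollars of its own year, the later group is more expensive even when it uses exactly the same resources. A raw two-sample test cannot separate that from an effect of the education program or the smartwatch.

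The bias has a known direction. It works against the intervention, so it could conceal a real saving or turn it into an apparent increase. Adjustment for case mix or for changes in care would not remove it, because it lies in the unit of measurement.

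**Working it through.** The documents give no cost figure, standard deviation, price growth rate, effect size or alpha, so there is no stated figure to reproduce. What follows is an illustration.

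**Inputs from the documents**
- Patients: 150 per period (Sample Size Calculation).
- Tests: two-sided t-test or Wilcoxon rank sum, unadjusted (Data Analysis).
- Comparator: January–June 2015 (Study Period).
- Prospective phase: undated. The two dates of 9 May 2019 put it about 4 years or more after the comparator.

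**Inputs assumed**
- Price growth *r*: 2–4% a year.
- Gap: 4–5 years.
- SD of log cost: 0.9, with a range of 0.6–1.0; lognormal costs.
- Two-sided alpha: 0.05.

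**Step 1. Drift with no change in resources:** (1 + *r*)^years − 1
- 2% for 4 years: 1.02^4 = 1.082, or +8.2%
- 3% for 4 years: 1.03^4 = 1.126, or +12.6%
- 4% for 5 years: 1.04^5 = 1.217, or +21.7%

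**Step 2. What happens to a true 10% saving:** 0.9 × (1 + *r*)^years − 1
- 0.9 × 1.0824 − 1 = −2.6%
- 0.9 × 1.1255 − 1 = +1.3%
- 0.9 × 1.2167 − 1 = +9.5%

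The real saving that drift would exactly cancel is 1 − 1/(1 + *r*)^years: 7.6%, 11.2% and 17.8%.

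**Step 3. Chance of a significant difference with no real change.** Both planned tests were simulated on lognormal costs, 150 v 150. Results are good to about one percentage point.

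| Drift | t-test, log-SD 0.9 | Wilcoxon, log-SD 0.9 |
|---|---|---|
| none | about 5% | about 5% |
| +8.2% | about 10% | about 11% |
| +12.6% | about 15% | about 19% |
| +21.7% | about 34% | about 44% |

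Over log-SD 0.6 to 1.0 and the same three drifts, the range is about 8–73% for the t-test and 9–79% for Wilcoxon. The low end is 2% for 4 years at log-SD 1.0; the high end is 4% for 5 years at log-SD 0.6.

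**Cross-check in closed form.** On the log scale the standard error is 0.9 × √(2/150) = 0.104. The shifts ln 1.082, ln 1.126 and ln 1.217 divided by 0.104 give z = 0.76, 1.14 and 1.89, hence 12%, 21% and 47%. A z-test on log cost is not a planned test. Its values lie slightly above the Wilcoxon figures and further above the t-test figures, as expected, so the simulated rates are the ones to use.

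**The case against.** Four objections have weight.

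- **Cost per case is peripheral.** It is in no hypothesis, objective, endpoint list or measurement list, and the same section says the data will be analysed for objectives and endpoints. This stands. A reader might infer that the study's main conclusions are at risk; they are not. But the section does commit to the comparison, and the data tool collects the variable.
- **Nominal dollars are not documented.** Business intelligence prepares the reports, and it could cost both cohorts on one basis. This also stands. A reader might infer a proven unit error, or that inflation will necessarily show as a cost increase caused by the intervention. The text supports only a conditional upward bias: the price basis is unstated, and a large enough real fall would still show as a fall.
- **The 2019 start is inferred.** The version date marks a revision and the log date marks a form; neither dates first enrolment. The inference is reasonable, because the text is in the future tense and the prospective phase requires the watch. It remains an inference, and the size of the drift depends on it.
- **This is one symptom of using a historical comparator.** In part, yes: a same-year comparator would remove most of the drift. Conversion would still leave other changes since 2015, and it would still set retrospective PD admissions against consenting, alert patients able to wear the watch. A reader should not infer that conversion makes the cost comparison fair. It removes one bias, which is specific to this variable and can be corrected without changing the design.

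Whether cost should be compared by means or by ranks is a separate choice of estimand and is not part of this point.

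**Conclusion.** The point holds as a conditional bias in an additional comparison. Applied to nominal dollars, the plan as written biases the later period's cost upward by about 8–22% under the assumed 2–4% a year over 4–5 years. A true 10% saving would be mostly hidden at the low end of that range and reversed at the high end. With no real change, a significant result would occur well above the 5% rate at the central log-SD of 0.9, and the rate varies widely with the assumed spread of costs. The rates, the gap, the log-SD and the alpha are all assumptions. The direction of the bias needs only two conditions: nominal figures and rising prices. The correction is worth making because it is cheap, but the primary knowledge endpoint and the listed secondary endpoints do not depend on it.

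**What to change.** In Prospective Study Period and Data Analysis:

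1. State whether the variable is cost or charge, and which system supplies it.
2. Before any comparison, convert both periods to one stated price year with a named index suited to that measure, or re-cost both cohorts on one cost basis.
3. Label the comparison exploratory, and note that conversion removes price change only.
4. If neither conversion nor re-costing is possible, drop cost per case and rely on length of stay, whose unit does not change.

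The cost is a line or two of text and one multiplication per record. The small downside is that a published index may not match this hospital's own price growth; re-costing on one basis avoids that but takes more work.

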### **Study Enrollment Procedure**

Patients with Parkinson's disease (PD) who meet inclusion criteria will be offered the opportunity to participate in the study. After obtaining informed consent, the patient will be enrolled in the study.

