## **Inclusion Criteria**

1. Adult patients diagnosed with primary and secondary diagnosis of Parkinson's disease
2. Patient 22 years old and older
3. Patients admitted to inpatient units and Center for Ambulatory Surgery
4. Alert and able to follow commands
5. Patient who agree to participate in the study

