## **Exclusion Criteria**

1. Patients less than or equal to 21 years of age
2. Patients who refuse or unable to wear the WatchRx smartwatch
3. Disoriented and unable to follow commands
4. Patients who are allergic to silicone, stainless steel and/or latex
5. Patients positive for Clostridium difficile and/or Candida auris

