#### **PD Medication Reconciliation:**

The Principal Investigator (PI) and Transitions of Care (TC) Pharmacists (sub-investigator(s)) will complete the admission medication reconciliation.

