#### **WatchRx System Enrollment:**

Using Internet Explorer web browser, the Principal Investigator and the TC Pharmacist (sub investigator(s) will complete the following:

- Enter the patient's information into the WatchRx Inc. Website interface to create the patient profile and PD medication regimen
- Register the patient into WatchRx web interface via website URL by entering the PD patient's name, unit number and room number.

- Enter the patient PD medication administration schedule as ordered
- Assign the WatchRx Smartwatch to the patient
- Review the WatchRx Smartwatch functions with the patient
- Review the Aware in Care Kit with the PD patient

The primary nurse will be asked to wear the WatchRx smartwatch. After obtaining verbal consent, the Principal Investigator and TC Pharmacist will review the patient's PD medication schedule in WatchRx smartwatch with the primary nurse.

The WatchRx web interface will activate reminder alerts from the patient's WatchRx Smartwatch to the primary nurse WatchRx smartwatch. Alerts reminders will send fifteen minutes before the PD medication is due. Medication reminder alerts will continue to be sent from WatchRx smartwatch worn by the patient to the WatchRx Smartwatch worn by primary nurse at 3-minute intervals for a period of 10 minutes or until the PD medication is administered.

At each end-of-shift and/or at handoff, the WatchRx smartwatch will be cleaned using Super SaniClothTM and the nurses will document completion of the WatchRx smartwatch cleaning procedure on the WatchRx Smartwatch cleaning log and verify by signing their names (Appendix F).

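### Prospective patients must still be in hospital at consent to be counted, 2015 patients need not, and the length-of-stay test ignores the difference

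*Combined protocol and SAP*

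**What the plan says.** **Prospective entry.** The Study Enrollment Procedure offers participation to eligible patients and then states: "After obtaining informed consent, the patient will be enrolled in the study". Under Inclusion Criteria these are "Patients admitted to inpatient units and Center for Ambulatory Surgery", and the list ends with "Patient who agree to participate in the study". Exclusion Criteria remove "Patients who refuse or unable to wear the WatchRx smartwatch", disoriented patients, and patients with either of two named infections.

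**Steps described after enrolment.** The investigator and pharmacist "will complete the admission medication reconciliation". WatchRx System Enrollment then lists tasks that include "Assign the WatchRx Smartwatch to the patient". Neither step has a time limit, and neither is stated as a condition of entry.

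**2015 entry.** The Retrospective Study Period reads "Data collection of adult patients admitted with a primary and secondary diagnosis of" Parkinson's disease, January to June 2015, extracted from the electronic record. No minimum stay is given. The protocol does not say which eligibility criteria apply to these records.

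**Analysis.** Length of stay is a secondary endpoint, and the Prospective Study Period section lists it among the outcomes to be compared. Data Analysis says: "Comparison of continuous variables between any independent groups will be examined using two-sided t-test or two-sided Wilcoxon rank sum test". No time origin for stay, delayed entry, landmark or covariate adjustment is mentioned. Limitations names only the single site and the convenience sample.

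**The concern.** The entry rule in one phase depends on the outcome being compared. A prospective patient is observed only if the stay lasts at least until consent; a 2015 patient is observed whatever the stay. This is left truncation in one group only. Neither the t-test nor the rank-sum test corrects for it.

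With stay counted from admission, the prospective group loses its shortest stays. A real shortening could be hidden, or a lengthening reported that did not occur. If stay were instead counted from enrolment in the prospective group and from admission in 2015, the error would favour the intervention. The undefined origin therefore matters as well.

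Falls, medication errors and positive screens are listed as numbers, with no patient-day or dose denominator, so any artificial difference in stay carries over into those counts. For the WatchRx hypothesis (Ho3), doses and events before the watch is active carry no watch exposure but would be counted in the intervention phase.

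**Working it through.** The plan has no figure to reproduce. Its 150 + 150 = 300 patients are a convenience sample with no power inputs, and no mean stay, SD or time to consent is given.

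**Assumptions (not in the documents).** Stay L is log-normal with median m = 3 to 5 days and log-SD σ = 0.7 to 0.9. Consent occurs at a fixed time c after admission. There is no true effect. Tests are two-sided at 5%.

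**Formulas.** With z = ln(c/m)/σ:
- share of patients lost: Φ(z)
- mean of all stays: E[L] = m·exp(σ²/2)
- mean among those still in hospital at c: E[L | L > c] = E[L]·Φ(σ − z)/Φ(−z)

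**Worked case, m = 4, σ = 0.8.** E[L] = 4·exp(0.32) = 5.51 days. At c = 1, z = −1.386/0.8 = −1.733, the share lost is 4.2%, and the ratio is 0.9943/0.9584 = 1.037. At c = 2, z = −0.866, the share lost is 19.3%, and the ratio is 0.9522/0.8069 = 1.180. The last column is a simulation of 150 vs 150 with the rank-sum test (nominal 2.5% in that direction).

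| Consent at | Mean ratio, stay from admission | Mean ratio, prospective stay from enrolment | False "longer stay" |
|---|---|---|---|
| 0.25 day | 1.00 | 0.96 | 2% |
| 0.5 day | 1.00 | 0.91 | 2% |
| 1 day | 1.04 | 0.86 | 10% |
| 2 days | 1.18 | 0.82 | 83% |

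**Range over the assumptions.**
- c = 1: from 0.9986/0.9893 = 1.01 (m = 5, σ = 0.7) to 0.9830/0.8889 = 1.11 (m = 3, σ = 0.9).
- c = 2: from 0.9777/0.9047 = 1.08 to 0.9116/0.6738 = 1.35.
- c = 0.5: at most 1.02.
- The two-sided false-positive rate at 150 vs 150 is about 4% to 36% at 1 day and 28% to over 99% at 2 days.

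**Ambulatory surgery.** If an assumed 5% to 10% of stays last only 0.2 to 0.5 day, consent at half a day already raises mean stay by about 5% to 12%. A false "longer stay" result then occurs in roughly 11% to 43% of trials.

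**Exclusion acting in one phase only.** Suppose a share s of 2015 patients are disoriented with stays k times as long, and the prospective phase excludes them. The net ratio is then the truncation ratio divided by 1 + s(k − 1). With m = 4, σ = 0.8, s = 10% to 30% and k = 1.25 to 2, the divisor runs from 1.025 to 1.30:
- c ≤ 0.5: below 1 throughout, lowest 1.00/1.30 = 0.77
- c = 1: 1.037/1.30 = 0.80 to 1.037/1.025 = 1.01
- c = 2: 1.180/1.30 = 0.91 to 1.180/1.025 = 1.15

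**Check of the repair.** Requiring both groups to be in hospital at the same hour c returns the ratio to 1.00 and the error rate to about 5% in the truncation-only model. It does not remove an imbalance from exclusions applied to one phase.

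**The case against.** The strongest reply is that size and direction are both unknown. Every magnitude rests on an assumed stay distribution and a fixed delay, and the large error rates need consent at about 2 days. The mention of admission reconciliation hints at early contact, and with consent inside half a day the effect on ordinary inpatient stays is negligible. This stands, and it limits how firmly any number can be stated. It does not show that consent will be early, because no enrolment window is set.

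Three stronger readings are tempting, and the documents do not support them.
- A reader might infer that patients enter only after reconciliation and watch set-up. The text enrols at consent and describes those steps afterwards, so consent is the truncation point.
- A reader might infer that the 2015 group is every Parkinson's admission. Sample Size Calculation specifies a convenience sample of 150, and 433 admissions in 2014 imply about 433/2 = 217 per half-year. Some selection by an unstated rule is likely.
- A reader might infer that the whole comparison, event counts included, is biased against the intervention. The exclusions for disorientation and infection, if applied prospectively only, plausibly shorten stays and lower some counts. As shown above, the net ratio can fall on either side of 1.

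It is also fair to say that time before watch activation is not wholly unexposed. Prospective data collection starts after the education programme, so those patients meet trained staff from admission. Finally, length of stay is one of seven secondary endpoints, and the primary endpoint, clinician knowledge, is untouched.

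**Conclusion.** The point holds in this form. Entry to the prospective phase requires being in hospital at consent, entry to the 2015 phase states no such condition, and the planned tests ignore it. Taken alone and counted from admission, the truncation lengthens prospective mean stay by about 1% to 11% for consent at 1 day and 8% to 35% at 2 days. At half a day or less it is negligible, unless same-day surgery stays are in the sample. These figures depend on the assumed log-normal stays and fixed consent time. The sign of the net bias in the full comparison is undetermined. That is a reason to measure and remove this component, since a bias of unknown sign is no safer than one of known sign. This is a cheap improvement to a secondary analysis and does not threaten the primary endpoint.

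**What to change.** 1. Define length of stay from admission in both phases.
2. Record hours from admission to consent and to watch activation.
3. Analyse stay in one of two ways. Either use one common landmark hour, keeping only patients still in hospital then in both phases and, prospectively, those who consented by then. Or model time to discharge with delayed entry at consent for prospective patients and entry at hour 0 for 2015 patients.
4. Apply the eligibility criteria that a chart can verify to the 2015 records, and state whether ambulatory surgery stays are included in both phases.
5. Count falls, errors and positive screens from the same landmark in both phases, per patient-day or per scheduled dose.
6. Use watch activation only to define watch exposure for Ho3. Using it for the education-programme objective would discard time spent under trained staff.
7. Report patients screened but not enrolled, with their stays.

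**Cost.** SAP wording and one or two time stamps, some of which may already exist: WatchRx data are stored in real time, and the data collection tool has time fields for the wrist band and registry. The landmark analysis drops some short-stay 2015 records and late-consenting prospective patients. No new patients are needed. None of this removes the calendar gap between 2015 and the prospective phase.
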